4. SUBJECT SELECTION

4.1. Study Population

The study will enroll 1500 HIV-1 infected, treatment-experienced adult patients who have been prescribed maraviroc along with an optimized background antiretroviral therapy (OBT) regimen in usual clinical practice following the approved local label of maraviroc.

The internal comparator group will consist of 1500 HIV-1 infected, treatment-experienced adult patients receiving OBT who received an HIV-1 tropism assay as a screening test for eligibility to receive maraviroc in usual clinical practice but were not prescribed maraviroc. This group may include patients infected with dual/mixed tropic or CXCR4 tropic HIV-1 as well as patients infected with CCR5 tropic HIV-1.

The subject enrollment scheme is presented in [Appendix 2](#).

The study will be conducted at approximately 300 sites in multiple countries. Participating countries were chosen on the basis of extensive feasibility assessments and include: Belgium, Brazil, Canada, France, Germany, Greece, Italy, Portugal, Spain, United Kingdom, and United States. If required, additional countries may be added and some countries in this initially proposed list may be dropped. Countries will participate only after maraviroc is approved by Health Authorities in that country and is commercially available. Enrollment will be competitive and recruitment of subjects will terminate after the global target sample size is achieved. The expected numbers of subjects in the participating countries are provided in [Table 1](#). Initial enrollment goals set for each country will be redistributed if necessary. Barring unforeseen circumstances (eg, significant delays in marketing authorization approval in countries, marked delays in regulatory approvals of the study protocol in countries, etc.), enrollment is expected to commence in 1Q2008 and is anticipated to continue for approximately 30 months. The enrollment status will be continuously monitored by the Sponsor and the external Scientific Steering Committee overseeing the study. If required, the enrollment period will be extended to enroll the necessary sample size.

090177e1928d33f51Approved/Approved On: 07-Jan-2020 12:23 (GMT)

Table 1. Enrollment targets by country

Countries	Expected number of study subjects	Projected launch date for commercial Maraviroc
Belgium	80	March 2008
France	200	April 2008
Germany	223	October 2007
Greece	40	March 2008
Italy	140	March 2008
Portugal	35	April 2008
Spain	250	May 2008

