6.2. Follow-up Visits

There will be no protocol-mandated patient visits or laboratory tests in this observational, non-interventional study. Data on subject's vital status, continued use of maraviroc, and study endpoints will be obtained through follow-up with the treating physician according to the local HIV/AIDS treatment guidelines and routine medical practice. Medical records and other documentation, where applicable, will be obtained to adjudicate study endpoints according to the endpoint adjudication manual.

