7.4. Endpoint Evaluation

At each visit after enrollment, the enrolling physician/investigator or designee will report all study endpoints for the subjects using an endpoint notification form. These endpoints may be identified by the enrolling physician at a follow-up visit or reported to the enrolling physician by other treating physicians or health care facilities. For subjects lost to follow-up, survival status may be identified through standard measures used in cohort studies, such as alternate contacts and tracking mechanisms (eg, national or regional death certificate data) however, endpoints will not be collected for adjudication.

When any of the study endpoints are identified or diagnosed, the enrolling physician will report the occurrence using an endpoint notification form and obtain the relevant medical records necessary to adjudicate the endpoint. The enrolling physician may request hospital discharge forms and medical records or their summary as needed. Where necessary and applicable, subjects will be contacted by the physician to assist in obtaining medical or hospital records.

These documents will be forwarded by the enrolling physician to the designated CRO for review by the Endpoint Committee (EC) in a de-identified format with the subject's study number added. The detailed process and timeframe for this endpoint data collection is described in the study Endpoint Manual.

De-identified copies of records, with translations into English where necessary, will be collated by the CRO for EC review. The EC will adjudicate the endpoint based on a review of the copies of relevant medical and hospital records. Two committee members will review each set of records individually and classify them according to the diagnostic algorithms described in the Endpoint Manual for the study. If the two adjudicators differ in their opinion, a third adjudicator will be assigned. The operational case definitions of the study endpoints as well as the operational aspects of the adjudication process are described in the study Endpoint Manual.

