9.1. Sample Size

The sample size for the study was determined based on an extensive feasibility assessment in 28 countries, input from Pfizer country offices, and in consultation with the regulators. This number was estimated to be 3,000 subjects (1,500 patients receiving maraviroc and

1,500 patients not receiving maraviroc) to allow calculations of reliable and precise risk estimates.

Malignancies, myocardial ischemia or infarction and deaths (liver-related and all cause) occurring at any time during the 5-year follow-up period will be adjudicated and analyzed as study endpoints. Assuming up to 10% annual loss to follow-up, the 1,500 patients each receiving maraviroc or the anchor drug will contribute 5,836 person-years of observation for these study endpoints over a 5-year period (See Scenario 1 in [Appendix 3](#) for details) in each treatment arm. It is assumed that the expected incidence rates are 12.7 per 1000 person-years for malignancies,¹⁴ 3.5 per 1,000 person-years for myocardial infarction,¹³ 2.35 per 1,000 person-years for liver-related deaths,¹⁵ and 16 per 1,000 person-years for all cause mortality¹⁵ in the internal comparator group of patients not receiving maraviroc.

CDC category C AIDS-defining opportunistic infections, viral encephalitis, rhabdomyolysis and liver failure will be adjudicated and analyzed as study endpoints if they occur during the use of maraviroc or the anchor drug in the OBT arm or within 6 months following maraviroc or anchor drug discontinuation. Accounting for the expected rates of drug discontinuation in the two treatment arms over time and a 10% annual loss to follow-up, each study arm will accrue 2,875 person-years of observation for these study endpoints (See Scenario 2 in [Appendix 3](#) for details). It is assumed that the expected incidence rates are 3.5 per 1,000 person-years for liver failure,¹⁶ and 160 per 1,000 person-years for AIDS-defining opportunistic infections¹⁷ in the internal comparator group of patients not receiving maraviroc.

Based on these assumptions of equal person years of contribution in the maraviroc exposed and unexposed groups, using a two-tailed test with $\alpha=0.05$, and a power of 80%, the minimum detectable relative rates for various study end points are reported in Table 2.¹⁸

Table 2. Minimum detectable relative rates using a two sided test, $\alpha =0.05$, and a power of 80%

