#### **4.2. Statistical Decision Rules**

##### **4.2.1. Sample Size**

*The sample size for the study was determined based on an extensive feasibility assessment in 28 countries, input from Pfizer country offices, and in consultation with the regulators. This number was estimated to be 3,000 subjects (1,500 patients receiving maraviroc and 1,500 patients not receiving maraviroc) to allow calculations of reliable and precise risk estimates.*

*Malignancies, myocardial ischemia or infarction and deaths (liver-related and all cause) occurring at any time during the 5-year follow-up period will be adjudicated and analyzed as study endpoints. Assuming up to 10% annual loss to follow-up, the 1,500 patients each receiving maraviroc or the anchor drug will contribute 5,836 person-years of observation for these study endpoints over a 5-year period (See Scenario 1 in Appendix 3 for details) in each treatment arm. It is assumed that the expected incidence rates are 12.7 per 1000 person-years for malignancies, (Beral, V. et al, 2000) 5 per 1,000 person-years for myocardial infarction, (Friis-Moller, N, et al, 2003) 2.35 per 1,000 person-years for liver-related deaths, (Weber, R, et al 2006) and 16 per 1,000 person-years for all cause mortality (Weber, R, et al 2006) in the internal comparator group of patients not receiving maraviroc.*

*CDC category C AIDS-defining opportunistic infections, viral encephalitis, rhabdomyolysis and liver failure will be adjudicated and analyzed as study endpoints if they occur during the use of maraviroc or the anchor drug in the OBT arm or within 6 months following maraviroc or anchor drug discontinuation. Accounting for the expected rates of drug discontinuation in the two treatment arms over time and a 10% annual loss to follow-up, each study arm will accrue 2,875 person-years of observation for these study endpoints (See Scenario 2 in Appendix 3 for details). It is assumed that the expected incidence rates are 3.5 per 1,000 person-years for liver failure, (Friis-Moller, N., Kirk O, Reiss P, 2003) and 160 per 1,000 person-years for AIDS-defining opportunistic infections (Kaplan, J.E., et al., 2000) in the internal comparator group of patients not receiving maraviroc.*

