## 8.2. Safety Analyses

All safety data will be subjected to clinical review and summarized according to Pfizer Data Standards and using the Safety Analysis Set. The format and algorithms described in Pfizer Data Standards documentation will be followed to produce summary tables and listings.

This study will provide data to calculate incidence rates on each of the study endpoints in the two study groups and will be analyzed as given below:

1. Descriptive statistics (ie, frequency, percent, mean, median, standard deviation as appropriate depending on data type) will be used to summarize characteristics (clinical and demographic) of patients enrolled in the study. (Potential variables include but are not limited to age, gender, weight, BMI, race, smoking classification, alcohol use (yes/no), HIV-1 RNA level, CD4+ T lymphocyte counts, duration of antiretroviral therapy, duration of HIV infection, number of failed regimens etc.).
2. Cumulative incidence rates and incidence-density rates of the study endpoints in the two groups will be reported along with respective 95% confidence intervals.
3. Subject discontinuation, loss to follow-up and total person-time of follow-up accrued in the study will be summarized.
4. Depending on data availability, appropriate subgroup analyses may be performed to further describe the rates of the study endpoints stratified by age group, gender, baseline CD4+ cell counts, baseline viral load, hepatitis C/hepatitis B serology, duration of maraviroc use, total duration of antiretroviral use, components of OBT etc.
5. In addition to the study endpoints, SAEs and drug-related adverse reactions reported during the study will be summarized in tables and listings.

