6. Crude and adjusted rate ratios with 95% confidence intervals will be calculated for each study endpoint comparing maraviroc-exposed patients to maraviroc-unexposed patients. Multivariate analysis techniques will be used as appropriate (e.g., Poisson regression model) to account for the baseline difference in the two study groups via propensity score technique. Specifically, since subjects are not randomized to treatment, there is a potential for imbalance in the above-mentioned important demographic and baseline characteristics between groups. To account for the imbalance between the two groups on the clinically important demographic and baseline characteristics, the confidence intervals will be adjusted for propensity score quintile. Specifically, propensity score for treatment membership (maraviroc exposed vs. maraviroc un-exposed) will be calculated for each subject from a logistic regression with the above mentioned covariates as predictors and study group membership as the outcome. Participants with similar propensity scores generally have similar distribution of the covariates on which the score is based. Participants will then be categorized into quintiles according to their propensity score. Four indicator variables will be created to represent the propensity score quintiles and will be used in the multivariate model as covariates along with the primary exposure variable i.e., exposure to maraviroc. Adjusting for propensity score quintile in this manner helps account for imbalances at baseline as discussed in D'Agostino (1998).
7. Appropriate survival analyses techniques (eg, Kaplan-Meier survival curves, Cox proportional hazards model) will be used to further analyze the data. The multivariate models will incorporate appropriate techniques referred to in section 4.2.3 to adjust for

potential survival bias.

8. In addition, incidence rates in patients receiving maraviroc in this study may be compared to those reported in comparable patients (ie, those with similar propensity scores and with the smallest Mahalanobis' distance between baseline values (D'Agostino, 1998) not using maraviroc in other HIV-1 infected cohort(s) such as EuroSIDA. The baseline characteristics of the patients (eg, number of failed regimens, CD4+ T lymphocyte counts) in this study will be used to identify comparable subjects from the external cohort(s).

The following data will be presented in standard safety summaries:

- *adverse events*

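### The planned confidence intervals ignore variation between about 300 sites, so the opportunistic-infection (OI) incidence-rate intervals are too narrow if site rates differ and results are meant to apply beyond these sites

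*Protocol*

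**What the plan says.** Protocol 4.1 sets the structure: "The study will be conducted at approximately 300 sites in multiple countries", with competitive enrollment. The SAP sample-size section (4.2.1) gives the total as "3,000 subjects (1,500 patients receiving maraviroc and 1,500 patients not receiving maraviroc"), which averages 10 patients per site.

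Follow-up is routine care. Protocol 6.2: "There will be no protocol-mandated patient visits or laboratory tests in this observational, non-interventional study". Protocol 7.4 says how events enter the study: at each visit "the enrolling physician/investigator or designee will report all study endpoints for the subjects using an endpoint notification form". The Endpoint Committee then adjudicates what it is sent. Two members review each case, with a third if they differ (Protocol 7.4), and review is blinded according to SAP 4.2.5.

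For analysis, SAP 8.2 item 2 says: "Cumulative incidence rates and incidence-density rates of the study endpoints in the two groups will be reported along with respective 95% confidence intervals". Item 6 says: "Multivariate analysis techniques will be used as appropriate (e.g., Poisson regression model) to account for the baseline difference in the two study groups". The terms it names are exposure and four propensity-quintile indicators. Item 7 adds Kaplan-Meier and Cox analyses. The covariates listed in SAP 6.2 are all patient-level, with an open clause for other relevant covariates if data exist.

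The only correlation either document mentions is recurrent events within one subject (Protocol 9.2, item 6).

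**The concern.** A Poisson interval for a rate allows for chance variation in the count and nothing else. Here sites may differ in case mix, in how often they see and test patients, and in how completely they notify events. Patients at one site then resemble each other more than patients at different sites, and the event total varies more than a Poisson count would. This is true even if no patient has more than one event, so it is a separate matter from recurrent events.

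Objectives 1 and 2 are absolute incidence rates in maraviroc users. A site effect does not cancel in a single-arm rate, so these are the quantities most exposed. SAP 4.1 states no hypotheses, so the estimates and their intervals carry the inference. They also feed the yearly regulatory reports, which SAP 3 bases on the Section 8.2 analyses.

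**Working it through.** **Inputs.**
- 300 sites (Protocol 4.1).
- 2,875 person-years per arm for OI, and an OI rate of "160 per 1,000 person-years for AIDS-defining opportunistic infections" (Protocol 9.1).
- Expected comparator events from Table 2: OI 460, all-cause death 93, malignancies 74, myocardial infarction 20, liver-related death 14, liver failure 10.
- Not in the documents, so assumed: SD of log site rate 0.3 to 0.5; CV of site size 0 (equal sites) or 1 (very uneven).

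**The plan's own figure.** Protocol 9.1 says that at "a power of 80%, the minimum detectable relative rates for various study end points are reported in Table 2". OI events: 0.160 × 2,875 = 460. Solving ln(RR) = (1.960 + 0.842) × √(1/460 + 1/(460·RR)) gives RR = 1.194, against the stated 1.1955. Table 2 is therefore reproduced closely by a calculation for independent patients, with no allowance for clustering.

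**Interval for one arm's rate.** With E events in the arm,

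inflation of variance = 1 + (E/300) × (1 + CV²) × (exp(SD²) − 1)

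coverage of a nominal 95% interval = 2Φ(1.96/√inflation) − 1

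For OI, E/300 = 1.533, and exp(SD²) − 1 is 0.094 at SD 0.3 and 0.284 at SD 0.5. The planned half-width is 1.96 × 160/√460 = 14.6 per 1,000 person-years.

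| SD | Site-size CV | Inflation | Half-width needed | Coverage as planned |
|---|---|---|---|---|
| 0.3 | 0 | 1.14 | 15.6 | 93.3% |
| 0.3 | 1 | 1.29 | 16.6 | 91.6% |
| 0.5 | 0 | 1.44 | 17.5 | 89.8% |
| 0.5 | 1 | 1.87 | 20.0 | 84.8% |

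**Other endpoints.** The same formula over the same four settings gives:
- all-cause death (93 events): 94.7% to 92.9%
- malignancies (74): 94.7% to 93.4%
- myocardial infarction (20): 94.9% to 94.6%
- liver-related death (14) and liver failure (10): 94.7% or higher

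**Interval for the OI rate ratio.** Let ρ be the between-site variance of the maraviroc share divided by 0.25. It is 0 if every site has the same share and 1 if each site recruits one arm only. Then

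inflation = 1 + 2ρ × (E/300) × (1 + CV²) × (exp(SD²) − 1)

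- ρ = 0: inflation 1, coverage 95%. The site effect cancels.
- ρ = 0.2 (moderately varying mix): equal sites 1.06 to 1.17, coverage 94.3% to 93.0%; site-size CV 1, 1.12 to 1.35, coverage 93.7% to 90.9%.
- ρ = 1: equal sites 1.29 to 1.87, coverage 91.6% to 84.8%; site-size CV 1, 1.58 to 2.74, coverage 88.1% to 76.3%.

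**Simulation check.** The set-up was 300 sites, lognormal site rates, gamma site sizes and 4,000 runs per setting. The arm share per site was even, Beta(2,2) (ρ = 0.2) or one-arm.
- Poisson interval for the OI rate, even mix: 93.6%, 92.2%, 90.3% and 84.0%, in the order of the table.
- Poisson interval for the rate ratio: about 95% with an even mix, 94.5% to 91.1% with the Beta(2,2) mix, 92.0% to 76.9% with one-arm sites.
- Site-clustered intervals: 93.6% to 95.6% in every setting.

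**The case against.** **Sites as fixed.** If inference is meant only for the participating sites, the sum of independent site counts is itself Poisson and the usual interval is valid. A simulation with site rates held fixed and both arms pooled gave 94.5% coverage at SD 0.3 and at SD 0.5; with random sites it gave 92% and 84%. This stands as a condition on the point. The documents do not say which target is meant. The stated aim, to characterise safety in a larger and more diverse population than the trials (Protocol 1.2.5), fits the wider one.

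**Mitigation.** Blinded central adjudication and monitoring at least yearly (Protocol 10) limit differences in classification. They do not remove case-mix differences, and adjudication cannot recover an event that a site never detected or notified. For adjusted ratios, the propensity score includes CD4 count, HIV-1 RNA, age and hepatitis status, so part of the case-mix variation is removed; the calculations above include no such adjustment. The SAP also offers Poisson regression only as an example, so a clustered variance is not excluded. It is not planned either.

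**Rate ratio.** A reader might infer that the OI rate-ratio interval is badly too narrow, with coverage near 76%. The documents do not support that. It needs every site to recruit a single arm. Under SAP Appendix 2, sites screen patients being considered for maraviroc and place each in an arm once the tropism result is known, and Protocol 4.1 defines the arms by what was prescribed. Mixed sites are therefore likely. Equal shares are not assured, because prescribing is usual practice and no arm quota per site is set.

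**Consequence.** With no hypotheses and no formal stopping rules, no prespecified decision turns on these intervals. That limits the priority of the point but not its correctness.

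**Conclusion.** The plan makes no allowance for between-site variation. If OI rates vary between sites and results are to apply beyond them, the intervals for the two arm-specific OI rates are too narrow. Under the assumed SD range, coverage is about 93% to 90% with equal sites and about 85% at SD 0.5 with very uneven sites. The direction is certain under those conditions. The size is not, because the documents give no between-site variance, site-size distribution or arm mix by site.

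For the OI rate ratio the effect is modest: about 92% to 95% with mixed sites, dropping to about 91% only when SD 0.5, uneven sites and a moderately varying arm mix coincide. The one-arm figures are an extreme bound.

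A reader might also infer that every endpoint's interval needs correcting. The effect is small for death and malignancies (about 93% to 95%) and negligible for the rarer endpoints. This is a cheap improvement to the OI analysis, not a flaw that undermines the study, and it needs no change in sample size.

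**What to change.** In SAP 8.2 items 2, 6 and 7, state that the 95% intervals for the OI rates, rate ratio and hazard ratio use a sandwich variance clustered on site.

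Add a site- or country-stratified OI rate ratio as a sensitivity analysis. Where both arm mix and OI rate vary by site, site may also confound the ratio, and a sandwich variance widens the interval without moving the estimate. In simulation with ρ = 0.2, a site-stratified ratio covered 94% to 95%, against 93% for the unadjusted ratio.

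Keep the planned or exact Poisson intervals for the rare endpoints, where clustering is negligible and a sandwich variance is unreliable. Clustering is optional for death and malignancies.

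The cost is a short SAP addition, one option in the model code and one extra analysis. Site should already be known for every patient, so no new data are needed. The downside is somewhat wider OI intervals; if sites hardly differ, they will barely change.

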4.2. Inclusion Criteria

Subjects (male or female) must meet the following inclusion criteria to be eligible for enrollment into the study:

1. The subject is antiretroviral treatment experienced and is currently being considered for treatment with maraviroc;
2. Receive an appropriate HIV-1 tropism assay as a screening for eligibility to receive maraviroc within 14 weeks prior to enrollment (The 14-week window does not apply to patients who started maraviroc as participants of A4001050 or A4001063);
3. Provide signed and dated informed consent to enrolling physician indicating that the patient (or, legally acceptable representative) has been informed of all pertinent aspects of the study;
4. Of 18 years of age or older (or, minimum age as determined by local regulatory authorities or as dictated by local law) at the time of screening;
5. Provide signed and dated informed consent to allow the enrolling physician access to medical, hospital and vital statistics records as appropriate;
6. Provide information on at least one alternate contact person (preferably the legal next of kin) who can be contacted regarding the patient's whereabouts and survival status, should the patient be lost-to-follow-up over the course of the study;
7. Acknowledge that in case of his or her death, the next of kin may be approached for a medical records release form if needed;

09017e1928d33f51Approved/Approved On: 07-Jan-2020 12:23 (GMT)

8. Provide Social Security Number (applicable to U.S. participants) or other national identification number or national health insurance number, as available and allowed by local law. **This information will only be used to search appropriate national or regional cancer and vital status registries for incidences of malignancies and deaths.**

